10.2 Determination of Sample Size

The estimated number of participants is 10 which is considered as sufficient in order to assess the feasibility of the study. Taking into account the meta-analyses on HRVB that reported large effect sizes (Hedges' $g > .81$) and the fact that we will conduct one-tailed tests, 10 patients is enough to have appropriate statistical power.

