2.3 Clinical Evidence to Date

Qualitative reviews indicate the effectiveness of HRVB in reducing stress and anxiety (Futterman & Shapiro, 1986; Gevirtz, 2013; Tabachnick, 2015). Earlier this year, a meta-analysis (Goessl et al., 2017) identified 24 studies (including 484 participants) using a HRVB program in order to reduce stress and anxiety. HRVB programs varied in intensity ranging from 1 to 50 sessions. Large effect sizes (Hedge's $g=.83$) were observed both in group comparisons (HRVB vs control conditions such as treatment as usual, waiting list, shame-biofeedback, and progressive muscle relaxation) and in time effects (pre-post intervention, Hedge's $g=.81$). These results indicate that HRVB is a promising intervention program in increasing HRV and thus decreasing stress and anxiety.

Considering using a HRVB program in order to reduce maternal stress due to a preterm delivery, to date, there are no existing studies. However, a pilot study using a HRVB program in women ($n=15$) suffering from perinatal depression indicated reductions in anxiety and depression symptoms (Beckham et al., 2013), suggesting promising effects in the perinatal period. Further studies are thus warranted in perinatology. Authors of the meta-analysis cited above (Goessl et al., 2017) concluded that HRVB is related to a large reduction of self-reported stress and anxiety and is therefore a promising intervention. However, authors also highlighted the need of better-designed studies including a robust control condition (accounting for the number of contacts with a therapist, for instance) and an assessment of

both short- and long-term effects.

Accordingly, in this feasibility study, we aim to examine the efficacy of a HRVB program on physiological (i.e., HRV) and psychological (i.e., perceived stress and anxiety) stress in mothers who delivered prematurely. We aim at assessing the feasibility of such an intervention program on such individuals in order to compile preliminary data for a bigger scale project.

So far, no clinical trial about HRVB in preterm population (<https://clinicaltrials.gov>) has been registered.

2.4 Dose Rationale / Medical Device: Rationale for the intended purpose in study (pre-market MD)

Based on a manual (Lehrer et al., 2000), on the recommendations of [name] (an international expert of HRVB) as well as on advice from [name] (the Swiss representative of Mindmedia), the HRVB will be provided daily for 2 weeks.

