4.2 Secondary Outcomes

HRV (i.e., root-mean square differences of successive R-R intervals), perceived stress, and mental health (anxiety, depression, PTSD).

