5. STUDY DESIGN

5.1 General study design and justification of design

Ten mothers who delivered prematurely at the maternity ward of CHUV will be invited to undertake a HRVB program. The HRVB program consists of a breathing technique to be performed 20 min daily over the course of two weeks. Physiological (i.e., HRV) and psychological (i.e., self-reported stress and anxiety) stress will be assessed pre- and post-intervention.

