10. STATISTICAL METHODS

10.1 Hypothesis

H0: The HRVB program will not show to be feasible and efficient in terms of increasing HRV and reducing stress, anxiety and/or depression.

H1: The HRVB program will show to be feasible and efficient in terms of increasing HRV and reducing stress, anxiety and/or depression.

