10.4 Planned Analyses

Acceptability of the study protocol and intervention as well as satisfaction will be reported descriptively. The inferential analyses will consist in comparing variables (HRV and mental health symptoms) from baseline to post-HRVB intervention using non-parametric Kruskall-Wallis tests. By convention, statistical significance will be set at .05.

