10.4.1 Datasets to be analysed, analysis populations

Data from participants who completed the study will be analysed. Drop out data will be used only for descriptive purposes.

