10.5 Handling of missing data and drop-outs

We will analyze data only from participants who completed the study. Missing data from drop out participants will not be replaced but it will be documented.

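### Section 10.2 rests its power claim on one-tailed tests, but section 10.4 plans Kruskal-Wallis tests, which have no direction and ignore that the same women are measured twice

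*Combined protocol and SAP*

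**What the plan says.** - **Hypothesis (10.1).** The alternative is directional: "The HRVB program will show to be feasible and efficient in terms of increasing HRV and reducing stress, anxiety and/or depression".
- **Design (5.1).** There is one group of ten mothers, each measured twice: "Physiological (i.e., HRV) and psychological (i.e., self-reported stress and anxiety) stress will be assessed pre- and post-intervention".
- **Sample size (10.2).** Ten is first called sufficient for feasibility. A second sentence then claims power, citing Hedges' g above .81 and "the fact that we will conduct one-tailed tests, 10 patients is enough to have appropriate statistical power". It gives no power value, outcome, pre-post correlation or named test.
- **Source of the effect size (2.3).** The meta-analysis is reported as g = .83 for group comparisons and g = .81 "in time effects (pre-post intervention"). It is described as covering programmes meant to reduce stress and anxiety.
- **Planned test (10.4).** HRV and symptom scores are compared "from baseline to post-HRVB intervention using non-parametric Kruskall-Wallis tests" at .05, with no sidedness stated.
- **Who is tested (10.4.1, 10.5).** "We will analyze data only from participants who completed the study"; "Drop out data will be used only for descriptive purposes".
- **Outcomes (4.2).** Besides HRV, the list is "perceived stress, and mental health (anxiety, depression, PTSD").

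**The concern.** The two sections do not describe the same analysis. Section 10.2 relies on a one-tailed test. Section 10.4 names an omnibus rank test that has no direction and assumes independent groups, although the baseline and post-intervention values come from the same women. When the two values are positively correlated, ignoring the pairing leaves the variation between women in the error term. The test then becomes conservative and usually loses power.

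The power sentence has further gaps. It counts all ten women although only completers are tested. Section 2.3 gives no separate effect size for HRV, depression or PTSD.

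The primary outcomes are not at stake, because they are descriptive. The error also runs towards missing an effect, not towards false claims of benefit. But section 2.3 says the data are to prepare a larger project, and section 10.2 invites the reader to take a non-significant pre-post result as informative.

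**Working it through.** **Inputs.** From the documents: n = 10 pairs, effect .81, level .05. Assumed, because the documents are silent: normal data, pre-post correlation r from 0 to 0.8, and 80% as the power benchmark. The scale of .81 is not stated, so both readings are shown: raw-SD units, and SD-of-change units (d_z). They are linked by d_z = d_raw / √(2(1−r)) and coincide at r = 0.5.

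**Step 1: can N = 10 be reproduced?** For a one-sided paired test by normal approximation, n = ((1.645 + 0.842)/0.81)² = 9.4, rounded up to 10. Power at n = 10 is Φ(0.81·√10 − 1.645) = Φ(0.917) = 82%. The noncentral t distribution gives 76% one-sided (11 women for 80%) and 63% two-sided (15 women for 80%). So N = 10 roughly fits a one-sided paired test, which 10.4 does not name.

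**Step 2: power of the planned and paired tests.** Kruskal-Wallis uses the chi-square reference with 1 df (one-tailed form: z > 1.645). It was simulated with 200,000 bivariate normal data sets, and a separate run of 100,000 agreed to within half a percentage point. Paired t is from the noncentral t. Signed-rank uses exact critical values (attained one-sided level .042).

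Effect .81 in raw-SD units, n = 10:

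| r | KW as planned | KW one-tailed | Signed-rank one-sided | Paired t one-sided |
|---|---|---|---|---|
| 0 | 40% | 53% | 46% | 51% |
| 0.3 | 38% | 54% | 58% | 64% |
| 0.5 | 37% | 55% | 72% | 76% |
| 0.7 | 37% | 57% | 89% | 92% |
| 0.8 | 37% | 60% | 97% | 98% |

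Effect .81 in SD-of-change units, n = 10 (the paired tests do not depend on r: signed-rank 71-72%, paired t 76%, both one-sided):

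| r | KW as planned | KW one-tailed |
|---|---|---|
| 0 | 66% | 78% |
| 0.3 | 52% | 67% |
| 0.5 | 37% | 55% |
| 0.7 | 18% | 34% |
| 0.8 | 8% | 19% |

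**Step 3: real level of the planned test.** With no true change, the nominal 5% Kruskal-Wallis test rejects 5.2%, 2.4%, 1.2%, 0.3% and 0.1% of the time at r = 0, 0.3, 0.5, 0.7 and 0.8.

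**Step 4: completers only.** With d_z = .81, one-sided paired t power falls from 76% with 10 women to 72%, 66% and 60% with 9, 8 and 7.

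**Step 5: the mechanism, in a made-up and deliberately extreme example.** Ten baseline scores are 10, 13, …, 37, and every woman improves, by 3.0, 3.1, …, 3.9 points. The rank sums are 91 and 119, so H = (12/420)(91²/10 + 119²/10) − 63 = 1.12 and p = 0.29. The one-sided exact signed-rank test gives p = 1/1024 = 0.001. The pre-post correlation here is 1, so this shows what ignoring the pairing does, not the loss to expect.

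**The case against.** The strongest reply is that the power sentence is not an arithmetic error. N = 10 follows from a one-sided paired approximation at 80%, and 10.2 cites the effect size as well as the sidedness. Silence on sidedness in 10.4 could be filled from 10.2, and with two sets of values Kruskal-Wallis is equivalent to a rank-sum test, which has a one-tailed form. All of that is true. It does not reconcile the sections: the named test remains non-directional and unpaired, and even its one-tailed form has only 53-60% power in raw-SD units.

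The 80% benchmark is mine, and the signed-rank test also misses it in SD-of-change units and, in raw-SD units, up to r = 0.5. The fair contrast is therefore between the tests, about 37% against 72% at r = 0.5. The statement that Kruskal-Wallis stays below 80% throughout holds at exactly .81. Section 10.2 says above .81, and in the single most favourable cell (one-tailed, r = 0, SD-of-change units) power is 79.6% at .83 and 81.3% at .85.

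The power sentence could be rewritten instead of deleted. That would need a scale for .81, a correlation and an outcome, none of which the documents supply. Section 2.3 does mention increased HRV in its conclusion, but gives no figure for it.

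Two points stand as limits of the remedy. Calling the comparisons exploratory sits uneasily with the efficacy wording in 3.1, 3.3 and 10.1. And one-sided tests on six measures (RMSSD, HF, PSS, PCL-5, STAI, BDI) carry a multiplicity cost: at .042 each, 1 − 0.958⁶ = 23% for at least one false positive if they were independent.

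**Conclusion.** The concern holds. The test on which 10.2 bases its claim is not the test in 10.4, and the test in 10.4 does not suit paired data. If the plan is followed as written and .81 is in raw-SD units, that effect would be missed about 6 times in 10 with all ten women completing, or 4 to 5 times in 10 if the test were made one-tailed. The gain from pairing appears from about r = 0.3 upward; at r = 0 there is none. These figures assume normal data and correlations of 0 to 0.8. Because neither the scale of .81 nor the correlation is documented, no single power figure can be defended for either test. This should be corrected before analysis, but it does not threaten the feasibility results.

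**What to change.** **Section 10.4.** Replace the Kruskal-Wallis tests with: *Each outcome's change from baseline to post-intervention will be tested with a one-sided exact Wilcoxon signed-rank test at .05 (increase for HRV, decrease for symptom scores). Zero changes are dropped from the ranking and their number is reported; ties are handled with the exact conditional distribution.* This also puts the one-tailed choice where the analysis is defined.

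**Section 10.2.** Keep n = 10, delete the power sentence, and write: *The sample size rests on feasibility; the pre-post comparisons are exploratory and no statistical power is claimed for them.* The efficacy wording in 3.1, 3.3 and 10.1 should be read over for consistency with this.

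**Check on tied scores.** With changes rounded to whole points, zeros dropped and an assumed SD of change of 2, 4 or 7 points (6,000 replicates), the proposed test keeps 71-73% power at d_z = .81 and a null level of 3.8-4.9%.

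**Cost.** A short text change in each of the two sections and the loss of a favourable power claim; no extra patients, visits or data. If the pre-post correlation were near zero, the signed-rank test would have slightly less power than a one-tailed Kruskal-Wallis test (46% against 53% in raw-SD units).

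### Section 10.2 claims appropriate power with 10 patients, but the unpaired, non-directional test in 10.4 and the completers-only analysis do not deliver it

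*Combined protocol and SAP*

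**What the plan says.** Section 10.2 gives two justifications for ten participants. The first is feasibility: "The estimated number of participants is 10 which is considered as sufficient in order to assess the feasibility of the study". The second is power. It cites Hedges' g above .81 and the direction of testing, and concludes: "we will conduct one-tailed tests, 10 patients is enough to have appropriate statistical power". No power value, outcome, test, pre-post correlation or drop-out allowance is stated.

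The effect size comes from the meta-analysis in section 2.3. It covered studies "using a HRVB program in order to reduce stress and anxiety" and found a group effect of g = .83 and large effects "in time effects (pre-post intervention, Hedge's $g=.81". Section 2.3 does not say whether the pre-post g is scaled by the raw SD or by the SD of the change.

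Section 10.4 plans to compare HRV and mental health variables between baseline and post-intervention "using non-parametric Kruskall-Wallis tests" at the .05 level, and does not mention one-tailed testing. On the analysis set, 10.4.1 says: "Data from participants who completed the study will be analysed". Section 10.5 repeats the restriction to completers and rules out replacing the missing data of drop-outs.

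**The concern.** The power statement and the analysis plan describe different analyses. Section 10.2 reasons from a pre-post effect tested in one direction. Section 10.4 names a test that ignores the pairing and has no direction. On two samples, Kruskal-Wallis is in effect the two-sided rank-sum test. Section 10.2 also counts ten mothers as ten analysable pairs, although drop-out is itself a primary outcome (4.1, 8.2.1) and only completers enter the tests. Section 6.3 may remove further mothers from the analyses for low training use.

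What is at stake is how the efficacy results will be read. Efficacy appears in the overall objective (3.1) and the hypotheses (10.1), and the study is meant to inform a larger project (2.3). If the tests carry a label of appropriate power, a non-significant result can be mistaken for evidence that HRVB does not work, even when a real effect of the assumed size would often be missed.

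**Working it through.** **Inputs from the documents.** n = 10, one-tailed, g = .81 (10.2, 2.3); significance level .05 and Kruskal-Wallis (10.4); completers only (10.4.1, 10.5).

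**Assumptions, because the documents give no figure.** Normal data; a benchmark of 80% power; pre-post correlation r varied from 0 to .8; completers varied from 10 to 8; g read either in raw-SD units or in SD-of-change units. The two units are linked by d_z = g / sqrt(2(1 - r)), so they coincide at r = .5.

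**Step 1: where ten may come from.** For a paired one-sided test with .81 SD of change, the normal approximation gives n = ((1.645 + 0.842)/.81)² = 9.4, rounded up to 10. Power at n = 10 is Φ(.81 × sqrt(10) - 1.645) = Φ(0.916) = 82%. With the exact noncentral t (noncentrality 2.56, 9 df), power at n = 10 is 76%, and 11 pairs are needed for 80%. So ten is nearly reproduced, but only with a paired parametric one-sided test and no drop-out.

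**Step 2: the test that 10.4 names.** With n values at each time and N = 2n, H = 12/(N(N+1)) × (R₁²/n + R₂²/n) - 3(N+1), where R₁ and R₂ are the rank sums at the two times. The test rejects when H exceeds the 95% point of chi-square on 1 df. The one-tailed version uses the 90% point and requires the right direction. Simulated power (200,000 replicates, n = 10, g = .81):

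| r | raw-SD units: as named | one-tailed | SD-of-change units: as named | one-tailed |
|---|---|---|---|---|
| 0 | 40% | 53% | 66% | 78% |
| .3 | 38% | 54% | 52% | 67% |
| .5 | 37% | 55% | 37% | 55% |
| .7 | 37% | 57% | 18% | 34% |
| .8 | 37% | 60% | 8% | 20% |

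No cell reaches 80%. In raw-SD units with r as high as .95, the one-tailed version still gives only 68%. The reason is that the reference distribution assumes independent samples. With positively correlated pairs the test becomes too conservative: its actual error rate at a nominal 5% is about 1.2% at r = .5 and 0.3% at r = .7.

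**Step 3: completers only.** With 8 completers, the named test has 26-31% power in raw-SD units for r = 0 to .7, and about 45% if one-tailed.

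**Step 4: a paired one-sided .05 test instead.** Exact noncentral t, and signed-rank with exact critical values by simulation:

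| pairs | .81 SD of change (r = .5 in raw-SD units): t | signed-rank | raw-SD units, r = .7 (d_z = 1.046): t | signed-rank |
|---|---|---|---|---|
| 10 | 76% | 71% | 92% | 89% |
| 9 | 72% | 70% | 89% | 87% |
| 8 | 66% | 59% | 84% | 79% |

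At r = .3 in raw-SD units, ten pairs give 64% (t) or 59% (signed-rank).

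**Step 5: which outcomes the effect covers.** The g of .81 concerns stress and anxiety. Sections 4.2 and 10.4 also test HRV, and the mental health variables include depression and PTSD symptoms. This protocol gives no planning effect for those three.

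**The case against.** The strongest reply is that this is a feasibility study. The primary objective (3.2) is acceptability and satisfaction, reported descriptively (10.4). Efficacy is secondary (3.3), and the first sentence of 10.2 justifies ten on feasibility alone. All of that stands. It limits the severity and rules out asking for more patients. It does not make the power sentence true.

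It can also be said that 10.2 promises only appropriate power, so 80% is the reviewer's benchmark. That is correct, and it is marked as an assumption. But under the raw-SD reading the named test misses an effect of the assumed size about 60% of the time, which is hard to call appropriate on any usual standard.

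A third reply is that the effect size itself is reasonable: a paired one-sided test with ten pairs comes close to 80% (step 1). This also stands. A reader might infer that g = .81 is too small to support ten patients, or that the loose g > .81 is what breaks the claim. The documents do not support that: using .83 moves the paired t at ten pairs only from 76% to 78%.

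Finally, a reader might infer that 80% is out of reach unless all ten mothers complete. That does not follow. In raw-SD units with r about .7, a paired t has 84% power with 8 pairs. The documents give neither r nor the unit of g, so this case can be neither claimed nor excluded. It requires a paired test, which the plan does not name.

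**Conclusion.** The power statement in 10.2 is wrong as written. With the test named in 10.4, power for ten mothers is about 37-40% (53-57% one-tailed) if g is in raw-SD units and r lies between 0 and .7. If g is in SD-of-change units, it falls from 66% at r = 0 to 8% at r = .8. Neither reading reaches 80%, even one-tailed.

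The main cause is the unpaired, non-directional test. The second is the completers-only analysis with no drop-out allowance: at .81 SD of change, going from 10 to 8 pairs lowers paired power from 76% to 66% (t) or from 71% to 59% (signed-rank). These figures rest on normal data, an assumed r, an assumed unit for g and an assumed 80% benchmark.

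The point should be fixed, but it does not threaten the study: the primary feasibility objective and its justification of ten participants are untouched.

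**What to change.** Three linked edits are needed. Changing 10.2 alone would leave a power figure for one test beside a plan for another.

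- **Section 10.4:** replace Kruskal-Wallis with a paired test, for example the Wilcoxon signed-rank test, one-sided at .05 as 10.2 says, with the direction stated for each outcome.
- **Section 10.2:** replace the power sentence with, for example: *The study is sized for feasibility and is not formally powered for efficacy; the tests are exploratory. Assuming a pre-post effect of .81 SD of change and one-sided 5%, the signed-rank test has about 71% power with 10 complete pairs and 59% with 8. This protocol gives no planning effect for HRV, depression or PTSD. A non-significant result is not evidence of no effect.*
- **Section 10.2:** write the pre-post effect as g = .81, matching 2.3.

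The cost is a few sentences in two sections and a less favourable stated power. No patients, visits or data are added.

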10.3 Statistical criteria of termination of trial

No criteria for the termination of the trial are a priori determined for this feasibility study.

10.4 Planned Analyses

Acceptability of the study protocol and intervention as well as satisfaction will be reported descriptively. The inferential analyses will consist in comparing variables (HRV and mental health symptoms) from baseline to post-HRVB intervention using non-parametric Kruskall-Wallis tests. By convention, statistical significance will be set at .05.

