8.2.4 Assessments in participants who prematurely stop the study

If a participant drops out from the study, an interview will be done to examine the reason of consent withdrawal if the participant agreed to explain her withdrew from the study. The data acquired within the study will be described in the grant proposal.

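### Efficacy is to be reported only as significance at .05 on at most ten pairs; no pre-post change, SD of change or interval is planned for the larger project

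*Combined protocol and SAP*

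**What the plan says.** Section 10.4 has two parts. Acceptability and satisfaction are to be described. HRV and mental-health scores are to be compared from baseline to post-intervention with Kruskal-Wallis tests, and "By convention, statistical significance will be set at .05". Nothing else is planned for the efficacy variables.

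Section 10.2 states that "The estimated number of participants is 10" and that "we will conduct one-tailed tests". It cites a pooled standardised effect above .81 and concludes that "10 patients is enough to have appropriate statistical power", without giving a power figure. Sections 10.4.1 and 10.5 restrict the analysis to participants who complete the study, so ten pairs is a maximum.

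On purpose, section 3.3 makes efficacy the secondary objective, and section 2.3 says feasibility is being assessed "in order to compile preliminary data for a bigger scale project". Section 8.2.4 adds "The data acquired within the study will be described in the grant proposal", but that sentence stands under the heading for participants who stop early.

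**The concern.** Someone planning a larger project needs to know, for each outcome, how far it moved, how variable the movement was, how strongly baseline and post values correlate, and how uncertain all of this is at n = 10. A list of p-values supplies none of it.

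A significant result would not tell the planner whether the change could be trivially small. A non-significant one would not tell them whether a useful change had been excluded. Section 8.2.2 lists six measures (RMSDD, HF, PSS, PCL-5, STAI, BDI), and section 10.1 words the hypothesis as stress, anxiety and/or depression. With no other quantity planned, a reader may well be drawn to whichever measures cross .05. At this sample size those are the ones whose observed change tends to overstate the true change.

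**Working it through.** **1. Is an estimate planned anywhere?** The sections that could supply one are:
- 10.4: descriptive reporting covers acceptability and satisfaction only.
- 7.4: intention-to-treat description covers baseline information and amount of training, for withdrawn or non-compliant participants.
- 10.4.1 and 10.5: drop-out data are described and missing data documented.
- 11.2: descriptive analyses serve to check the range of values before testing.
- 2.3 and 10.2: effect sizes appear only as inputs from the literature.

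None plans a mean or median change, an SD of change, a correlation or an interval.

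**2. The plan's own figure.** Inputs: effect .81 (2.3 and 10.2), one-tailed (10.2), alpha .05 (10.4). Two assumptions are needed: power .80, and .81 read as mean change divided by SD of change.
- Normal approximation: n = ((1.645 + 0.842)/.81)² = 9.4, rounded up to 10.
- Noncentral t: power at n = 10 is .76, and 11 are needed for .80.

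So the stated 10 is reproduced under those assumptions.

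**3. Precision with 10 pairs.**
- 95% half-width for the mean change: t(.975, 9)/√10 = 2.262/3.162 = 0.72 SD of change.
- A mean change of exactly zero would therefore have an interval of −0.72 to +0.72 SD.
- Observed standardised change .81: t = .81 × 3.162 = 2.56. Inverting the noncentral t gives noncentralities of 0.23 and 4.79. Divided by 3.162, the 95% interval is .07 to 1.51.
- 95% limits for the SD of change: √(9/19.02) = 0.69 and √(9/2.700) = 1.83 times the observed SD.
- If only 8 completed (illustrative), the half-width is 0.84 SD, the interval for an observed .81 is −.02 to 1.60, and the SD limits are 0.66 and 2.04 times the observed SD.

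**4. What selection on p < .05 would do.** Stand-in test: one-sided paired t-test on 10 normally distributed changes. Significance needs an observed standardised change of at least 1.833/3.162 = .58. The table comes from simulation; the ratio is the average mean change among significant results divided by the true mean change.

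| True standardised change | Proportion significant | Ratio for the mean change |
|---|---|---|
| .81 (cited for planning) | 76% | 1.14 |
| .5 (assumed) | 43% | 1.5 |
| .3 (assumed) | 22% | 2.3 |

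Sensitivity to the test:
- Two-sided paired t-test: 1.21 at .81 and 1.66 at .5.
- One-sided Wilcoxon signed-rank test: 1.16, 1.57 and 2.34 at .81, .5 and .3.
- Kruskal-Wallis as named, treating baseline and post values as separate groups, with the effect in raw-SD units and pre-post correlation from 0 to .7: 1.50 down to 1.24 at .81, and 2.56 down to 2.01 at .4.

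The stand-in does not exaggerate the problem.

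**The case against.** The strongest reply is that this is a feasibility study. Its primary outputs are eligibility, acceptance, compliance, drop-out and satisfaction. These are to be described, and none depends on a significance test. That stands: a reader might infer that the study fails its own purpose, and the documents do not support that.

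A reader might also infer that the data going to the larger project will be exaggerated. They need not be. The mean change over all results is not biased by testing; the overstatement belongs to results picked out because they were significant. Section 10.4 sets an alpha level and does not say that significance will decide which outcomes go forward. Section 8.2.4 does not close the gap, since it may concern only participants who stop early and speaks of describing data.

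The most tempting figure is that a later trial would be about eight times too small. In standardised units, the average significant result at a true .3 is .83, and (.83/.3)² = 7.7. That rests on an assumed .3, on a test the plan does not name, and on sizing the later trial from this single-arm standardised change. At the planning value of .81 the ratio is 1.14 for the mean change and 1.28 in standardised units, so the sample-size factor is 1.14² = 1.3 to 1.28² = 1.6. Section 2.3 also notes the need for a robust control condition. A controlled trial would be sized on a between-group difference, which a pre-post change cannot supply however it is reported.

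The omission survives all of this. With or without selection, no efficacy estimate or measure of its uncertainty is planned.

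**Conclusion.** The point holds as an analysis gap that should be closed before the data are analysed. Significance at .05 is the only planned efficacy output, and at most ten pairs cannot turn it into usable planning information. The mean change will be known only to ± 0.72 SD of change, and the SD itself only to between 0.69 and 1.83 times its estimate. These figures assume ten complete pairs and roughly normal changes; fewer completers would widen them.

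The overstatement is conditional. It needs selection on p < .05, which the plan does not prescribe, and its size depends on the unknown true change: small at .81, considerable at .3 to .5. Whether Kruskal-Wallis suits paired data, and how it fits with one-tailed testing, are separate questions.

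**What to change.** Rewrite the efficacy part of 10.4 so that estimation is the main output. For every secondary outcome, whatever its p-value, report:
- the paired change with a 95% confidence interval;
- the SD of change;
- the pre-post correlation;
- the number of pairs.

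Label the significance tests supportive or exploratory. Rules for sizing the larger trial belong in that trial's protocol and need not be set here.

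The cost is a few lines of text and a little more analysis of the same data, with no extra participants or visits. The intervals will be wide and the headline less striking than a p-value.
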